### 9.9.5. Dose Proportionality

Dose proportionality will be evaluated for Cmax, AUC0-12, AUC0-24, and AUC0-∞ for study arms in Phase I. Dose proportionality will be evaluated after dosing on Day 1 and Day 15, separately. A power model (regression of log-transformed data) will be fit on Day 1 and Day 15, separately, to describe the relationship between PK parameters (Cmax, and AUCs) and dose. Dose proportionality will be concluded when the ratio of dose-normalized geometric mean values (Rdnm) lies entirely within (0.80, 1.25), that is 90% CIs of the slope  $\beta$  lies entirely within  $(1+\ln(0.8)/\ln(r), 1+\ln(1.25)/\ln(r))$ , where  $r$  is a ratio that describes the dose range and is defined as the ratio of (highest dose/lowest dose). For each model, the predicted geometric mean PK parameter values, Rdnm, maximum proportional dose range ( $\rho_1$ ) and threshold dose ratio to reject proportionality ( $\rho_2$ ) will be reported based on the estimates from the power model [6].

Results for the dose proportionality analysis of all parameters will be shown also graphically.

## 9.10. Pharmacodynamic Analyses

PD analyses for hematological changes will include all patients who received at least 1 dose of AK-01 (i.e. belong to the FAS) and have PD data that is sufficient and interpretable, as determined by the sponsor. The hematology parameters will be analyzed as described in Section 9.8.3. Changes from baseline in white blood cell count, neutrophil count (total, i.e. segmented + banded), platelets hemoglobin and hematocrit will be compared to

- AUC0-12, Cmax and Cavg for Day 15

graphically by scatterplots displayed for each parameter. Pearson and Spearman correlation coefficients will also be calculated.

PD analyses for target engagement will include all patients who received at least 1 cycle of AK-01 and from whom samples are collected of sufficient quantity and quality for evaluation. Mitotic index based on skin and/or tumor biopsy will be presented by descriptive statistics of actual results and change from baseline, separately for results based on skin and tumor biopsy. All PD results will be listed.

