**Table 1. AK-01 Dose Modifications for Toxicity**

Toxicity	Dose Modification
QTcF Prolongation	
<Grade 2	Continue at current dose level.
Grade 2 (QTcF average of triplicate readings >480 msec)	Reduce dosing frequency without interruption. If the event recurs, the dose may be withheld. If the event recurs a third time, dosing may only continue with sponsor approval.

Grade 3 (QTcF average of triplicate readings >500 msec)	Withhold AK-01 for up to 14 days. If QTcF returns to within 30 msec of baseline or <450 msec within 14 days, treatment may be resumed at a reduced dosing frequency. If the event recurs a second time, the dose may again be withheld and resumed after 14 days providing the above criteria are met after 14 days. If a third occurrence is documented, treatment must be terminated.
Grade 4 (QTcF average of triplicate readings >500 msec or >60 msec change from baseline, and TdP or polymorphic ventricular tachycardia or signs/symptoms of serious arrhythmia)	Treatment should be terminated.
Other Non-Hematologic Toxicity	
Grade ≤2	Continue at current dose level.
Grade 3 (except alopecia, nausea, vomiting or diarrhea) not optimally managed per institutional guidelines	Withhold AK-01 until event returns to Grade 1 or baseline. The first time the event occurs, maintain the AK-01 dose level when dosing is resumed.  Each time the Grade 3 event recurs, withhold AK-01 until event returns to Grade 1 or baseline, then decrease AK-01 dosing frequency- when dosing is resumed. If the event recurs at 25 mg QD, the patient will be withdrawn.
Grade 4 (except alopecia, nausea, vomiting or diarrhea) not optimally managed per institutional guidelines	Patient will be withdrawn. Patient may not be rechallenged unless discussed with sponsor and approved by the SAC.
Hematologic Toxicity	
Platelets ≤Grade 1  ANC ≤Grade 1 on Day 1 and/or ANC ≤Grade 2 on Day 8 or 15	Continue at current dose level.

Platelets  $\geq$ Grade 2,  
ANC  $\geq$ Grade 2 on Day 1,  
ANC  $\geq$ Grade 3 on Day 8 or 15,  
and/or  
 $\geq$ Grade 3 platelets or ANC with  
spontaneous bleeding at any  
time

Withhold AK-01 until platelets  $\leq$ Grade 1 and ANC  
 $\leq$ Grade 1 (Day 1) or  $\leq$ Grade 2 (Day 8 or 15). Consider  
granulocyte colony stimulating factor (G-CSF) for low  
ANC. Decrease AK-01 dosing frequency when dosing is  
resumed.

Each time the Grade 3 event recurs, withhold AK-01  
until counts recover. Consider G-CSF for low ANC. If  

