## 5.6. Concomitant Therapy

All concomitant medication administered from the time of first dose until the last dose of IMP must be recorded, along with the reason for use and date of administration. This includes over-the-counter or prescribed medications, vitamins and herbal supplements.

All concomitant medication administered to treat an ongoing AE or serious adverse event (SAE) must be recorded until the events resolve, the events are no longer considered to be drug-related, the patient dies or is lost to follow-up, or a new treatment is initiated for the patient.

While on study, patients may be administered medications at the discretion of the investigator to treat AEs or as supportive care (e.g., anti-emetics, antibiotics, etc.).

BC patients on a stable regimen of bone health agents (e.g., selective estrogen receptor modulators, bisphosphonates, etc.) may continue treatment.

Hematopoietic growth factors (e.g., erythropoietin, G-CSF) may be administered in this study according to institutional guidelines except in Cycle 1 of Phase I. Hematopoietic growth factors will be allowed in Cycle 1 of Phase I if a patient experiences neutropenia that is declared a DLT.

Blood product transfusions will be permitted throughout the study

CCI

CCI

Other chemotherapy, investigational therapy, molecularly-targeted therapy and cancer-related hormone therapy will be prohibited within 14 days prior to study enrollment (6 weeks for mitomycin-C or nitrosoureas) and throughout the study. Biologic therapy and immunotherapy will be prohibited within 21 days prior to study enrollment and throughout the study.

Radiotherapy to non-target lesions will be permitted on study if approved by the sponsor.

Anticoagulants (e.g., oral anticoagulants, low molecular weight heparin), antiplatelets (e.g., acetylsalicylic acid, P2Y12 inhibitors), and nonsteroidal anti-inflammatory drugs (e.g., ibuprofen, naproxen) should be stopped prior to tumor biopsy according to institutional practice.

Any patient with questions regarding concomitant therapies will be asked to contact the investigator.

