### 6.2. Pharmacodynamic Evaluations

#### 6.2.1. Samples for Pharmacodynamic Evaluations

Hematology samples (see Appendix\_1) will be used to evaluate a variety of hematological parameters, including white blood cell count, neutrophil count, and lymphocyte count. Changes in hematological parameters may be compared across time points and to AK-01 PK.

In Phase I, pre-treatment and on-treatment skin biopsies will be mandatory for all patients (see Appendix 1). For all Phase I patients enrolled in the P2D confirmation cohorts (after identification of the MTD, see [Section 3.1.3](#)), pre-treatment and on-treatment biopsies of primary or metastatic tumor will also be required (see Appendix 1). For all patients enrolled in Phase II, tumor biopsies will be required from either a primary or metastatic tumor site. SCLC patients tumor biopsies will be required unless the primary or metastatic tumor site is inaccessible or a quality biopsy cannot be obtained. The initial tumor biopsy should be collected after the patients previously failed therapy and prior to C1D1, and the second biopsy should be collected at C2D8,  $\pm$  3 days. Archived specimen(s) from a diagnostic biopsy and/or surgery of the tumor may be requested instead of pre-treatment tumor biopsy as long as the biopsy was obtained after they had already failed previously therapy. Tumor samples may be used for both PD and molecular profile analyses (see [Section 6.3](#)).

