  - q. PK sampling will be performed in Cycle 1 of both Phase I and II at the following time points relative to the first dose on Day 1 and Day 15: 0 hours (pre-dose) and 1, 2, 4, 6, and 8-12 hours post-dose. Additional trough samples will be obtained prior to dosing on Day 2 and Day 8 of Cycle 1. The sampling schedule may be modified following review of PK data from the first cohort in Phase I to optimize collection times. A PK sample will also be obtained at the Discontinuation visit. A maximum of 3

additional PK samples may be drawn at other time points during the study, if warranted and agreed upon by both the investigator and the sponsor.

- r. A CT scan with IV contrast and assessment of tumor response by RECIST (v. 1.1, see Appendix 10) will occur within 1 week of the last dose of Cycle 2 and Cycle 4, and every 9 weeks ( $\pm$  1 week) thereafter for the duration of treatment. The schedule of tumor assessments will be maintained independent of any treatment schedule delays or changes. All CT scans will include the chest, abdomen and pelvis. For each tumor assessment, the date, method, and response evaluation will be recorded. Tumor response will not be evaluated at the screening CT scan (collected as the baseline). MRI may be performed instead of CT if a patient cannot tolerate CT contrast agents due to an iodine allergy. An individual patient will be monitored by the same methodology throughout the study. For patients that meet RECIST criteria for complete response or partial response, a confirmatory radiographic assessment will be obtained 4 weeks (+/- 5 days) after the response criteria was met.
- s. Dosing of AK-01 may continue until disease progression if the patient is receiving benefit and is experiencing no severe toxicity in the opinion of the investigator. Following Cycle 1, an entire cycle may be delayed or advanced by +/-1 day for administrative reasons, in which case it will be shortened (or lengthened) by 1 day, respectively.
- t. The discontinuation date will be recorded with the primary reason for discontinuation (if applicable). The patient will attend a Discontinuation visit as soon as possible after participation ceases.
- u. A CT scan and assessment of tumor response will be performed at the Discontinuation visit for patients who discontinue the study for reasons other than radiographic progression, and if a CT scan has not been performed within the prior 4 weeks.

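### The blood count correlation in SAP 9.10 uses only Day 15 exposure, which Table 1 may already have lowered because of the Day 8 count; add Day 1 exposure and name the count

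*SAP*

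**What the plan says.** **Analysis.** SAP 9.10 opens the comparison with "Changes from baseline in white blood cell count, neutrophil count (total, i.e. segmented + banded), platelets hemoglobin and hematocrit will be compared to" and lists as exposure measures "AUC0-12, Cmax and Cavg for Day 15". The output is scatterplots, and "Pearson and Spearman correlation coefficients will also be calculated". No visit, day or nadir is named for the count. The only data rule is that patients must "have PD data that is sufficient and interpretable, as determined by the sponsor".

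**Exposure data.** Protocol Appendix 1 schedules full Cycle 1 PK profiles "relative to the first dose on Day 1 and Day 15: 0 hours (pre-dose) and 1, 2, 4, 6, and 8-12 hours post-dose". SAP 9.9.4 derives the parameters for both days. Day 1 data are used alongside Day 15 for the ECG-exposure plots (SAP 9.8.5) and for dose proportionality (SAP 9.9.5), but not in 9.10.

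**What happens between the two profiles.** Appendix 1 schedules hematology on Days 1, 8 and 15 of Cycle 1. In the hematologic rows of Protocol Table 1, platelets at Grade 2 or worse, or a Day 8 ANC at Grade 3 or worse, lead to a hold and then to a lower dosing frequency on restart. At the Phase II dose that means 25 mg BID to 25 mg QD. Section 3.3.2 lets a hold run up to 21 days, and Appendix 1 keeps the patient on the visit calendar meanwhile. In Phase I, Section 3.1.1 also requires interruption after a DLT.

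**Supportive care.** Table 1 suggests considering G-CSF for low ANC. Section 5.6 allows growth factors, except in Cycle 1 of Phase I unless neutropenia is declared a DLT, and adds that "Blood product transfusions will be permitted throughout the study".

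**Lymphocytes.** Protocol 6.2.1 lists hematological parameters "including white blood cell count, neutrophil count, and lymphocyte count", as does the synopsis. The SAP 9.10 correlation leaves lymphocytes out, and SAP Section 2 does not declare the change.

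**The concern.** An exposure-response correlation assumes that exposure comes first and response follows. Here, for any patient who crosses a Table 1 threshold on Day 8, the order is reversed: the count decides the dosing, and the dosing decides Day 15 exposure. On Day 15 such a patient may be off drug with no usable profile, newly restarted, or on once-daily dosing. These are the patients with the steepest falls, so they carry most of the information about whether higher exposure lowers counts more.

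PK and PD characterization is a Phase II secondary objective, and neutropenia and thrombocytopenia head the list of potential adverse events in Protocol 1.3 and 3.3.1. At stake is whether the study report describes the relation between exposure and marrow effect correctly.

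**Working it through.** The documents state no expected correlation or power for this analysis, so there is no plan figure to reproduce. They also give no half-life and no share of patients held before Day 15. Everything below rests on assumed values; only the cohort size of 30 (Protocol 3.6) and the BID-to-QD step (Table 1) come from the documents.

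**1. What once-daily dosing does to Day 15 exposure.** The daily dose halves, from 50 mg to 25 mg, but each dose stays at 25 mg. In a one-compartment bolus model at steady state, the QD/BID ratio of AUC0-12 and of Cmax is (1 − e^(−12k)) / (1 − e^(−24k)) = 1 / (1 + e^(−12k)), with k = ln 2 / half-life. For a 12 h half-life this is 1 / (1 + 0.5) = 0.67.

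| Assumed half-life (h) | 3 | 6 | 12 | 24 | 48 |
|---|---|---|---|---|---|
| Ratio | 0.94 | 0.80 | 0.67 | 0.59 | 0.54 |

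A 40% drop (ratio 0.60) needs e^(−12k) = 2/3, a half-life of 12 × ln 2 / ln 1.5 = 20.5 h.

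**2. Size when the count precedes the hold.** Assumptions: 30 patients; log-exposure SD 0.5 between patients and 0.2 between days; count drop = 0.5 × (patient's log-exposure) + noise with SD 0.45; the patients with the largest drops are held after Day 8; 3,000 simulated trials. The implied underlying correlation is 0.5 × 0.25 / (√0.29 × √0.265) = 0.45. Mean Spearman coefficient with the drop (a positive value means more exposure, larger fall):

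| Held | Day 1 exposure | Day 15, held have no profile | Day 15, half missing, half 40% lower | Day 15, all held 40% lower |
|---|---|---|---|---|
| 1 of 30 | 0.42 | 0.40 | not split | 0.37 |
| 20% | 0.42 | 0.34 | 0.24 | 0.17 |

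Over the three treatments of held patients, the range is about 0.29 to 0.37 with 10% held and 0.08 to 0.30 with 30% held. If nobody is held, Day 15 exposure also gives 0.42, so the loss comes from the holds and not from the choice of day.

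**3. Does the direction always hold?** A second simulation used different assumptions: n = 30, 1,500 replicates, exposure CV 40% between and 20% within patients, underlying correlation 0.5, QD ratio 0.67. It is expressed as change from baseline, so the true sign is negative. Mean Pearson r is −0.42 both for Day 1 exposure and for Day 15 exposure with unmodified dosing. For Day 15 exposure when some patients are affected:

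| Count used; how affected patients enter | 1 of 30 | 10% | 20% | 30% |
|---|---|---|---|---|
| Day 8 change; missing | −0.39 | −0.36 | −0.33 | −0.30 |
| Day 8 change; on QD | −0.35 | −0.27 | −0.17 | −0.11 |
| Day 8 change; zero exposure | −0.17 | +0.12 | +0.36 | +0.50 |
| Day 15 change, half recovered; zero exposure | −0.34 | −0.24 | −0.14 | −0.05 |
| Day 15 change, fully recovered; zero exposure | −0.47 | −0.55 | −0.63 | −0.68 |

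Most rows shrink toward zero. One reverses sign, and one is exaggerated because zero exposure is paired with a recovered count. SAP 9.10 does not say which row applies.

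**The case against.** The strongest reply is that little depends on this analysis. It consists of plots and coefficients with no test or decision rule, and the protocol says only that the relation may be evaluated (synopsis; 8.1.3). The Phase II dose is already set and increases are not allowed (3.2). Marrow toxicity is captured separately by worst-post-baseline grade shift tables (SAP 9.8.3), by DLT and adverse event summaries, and by dose intensity by cycle (SAP 9.7.1). All of that stands, and it limits the priority of the point.

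The size is also unanchored. Only threshold crossings by Day 15 matter, Phase II runs at 25 mg BID, and the DLTs in Protocol 1.3 were at 50 and 75 mg. A hold rate of 20% is therefore an assumption. With 1 of 30 affected the shift is small, unless that patient is entered with zero exposure.

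Three stronger readings are tempting and not supported:

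- A reader might infer that the correlation must be biased toward zero, and so errs in the unsafe direction. That is the likeliest outcome, but sign reversal and exaggeration are both possible, and no dose decision rests on the result.
- A reader might infer that exposure is halved in reduced patients. That is true of the daily dose; AUC0-12 and Cmax may fall much less.
- A reader might infer that the SAP retains counts taken after G-CSF or transfusion. It has no explicit rule either way; the sponsor's judgment of what is interpretable could exclude them.

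On lymphocytes, Protocol 6.2.1 says changes may be compared with PK, so the omission is minor. It is still undeclared.

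**Conclusion.** The defect is in the text: the only exposure measure in the SAP 9.10 correlation can be altered by the outcome before it is measured, and the SAP has no rule for the patients concerned. The result is distorted, most likely toward zero. Under the assumed values, about 0.42 becomes 0.17 to 0.34 with 20% of patients held, and 0.37 to 0.40 with one in 30 held when that patient's profile is missing or lower. The true size and sign depend on three things the documents leave open: the count time point, how held patients enter (missing, zero or on QD), and the hold rate.

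This is a cheap improvement to a descriptive analysis that serves a Phase II secondary objective (exploratory in Phase I).

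**What to change.** In SAP 9.10:

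1. Name the count: for example, the change from baseline to Day 8, or the Cycle 1 nadir before any G-CSF or transfusion.
2. Make Day 1 AUC0-12 and Cmax the main exposure measures. They are already derived and precede any dose change.
3. Keep Day 15 exposure as a secondary analysis. State how patients held or reduced before Day 15 are entered, flag them on the plots, and report their number. If a version restricted to patients without a hold is shown, note that it selects on the outcome; it corresponds to the no-profile column above (0.34 against 0.42 with 20% held).
4. Add lymphocytes to the correlation, or declare the omission in SAP Section 2.

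The cost is SAP wording and a rerun of the same plots and coefficients on planned data. The downside is that Day 1 exposure does not reflect accumulation, and the Day 15 analysis does not fully make up for that.

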## 9.11. Molecular Profile Evaluation

The sponsor will not request any additional molecular profile evaluation.

## 9.12. Interim Analyses

Safety and other available data will be evaluated prior to dose escalation in Phase I as detailed in the Protocol. It is not part of this SAP.

In Phase II, once all patients within a cohort have completed at least 8 cycles of treatment, had disease progression, or discontinued AK-01, data analyses for that cohort may be performed. No formal interim data analysis is planned for this study.

## Appendix 1; TFL shells

See a separate document.
